6.4 Reporting of Pregnancy and Lactation to Merck

Although pregnancy and lactation are not considered adverse events, it is the responsibility of investigators or their designees to report any pregnancy or lactation in a subject (spontaneously reported to them), including the pregnancy of a male subject's female partner that occurs during the trial or within 12 months of completing the trial completing the trial, or 30 days following cessation of treatment if the subject initiates new anticancer therapy, whichever is earlier.

All subjects and female partners of male subjects who become pregnant must be followed to the completion/termination of the pregnancy. Pregnancy outcomes of spontaneous abortion, missed abortion, benign hydatidiform mole, blighted ovum, fetal death, intrauterine death, miscarriage and stillbirth must be reported as serious events (Important Medical Events). If the pregnancy continues to term, the outcome (health of infant) must also be reported.

Such events must be reported within 2 business days of investigator knowledge to Merck Global Safety. (Attn: Worldwide Product Safety; [contact])

6.5 Reporting Requirements for Adverse Events/Adverse Reactions

6.6 Serious Adverse Events

A serious adverse event is any adverse event occurring at any dose or during any use of Merck's product that:

- Results in death;
- Is life threatening;
- Results in persistent or significant disability/incapacity;
- Results in or prolongs an existing inpatient hospitalization;
- Is a congenital anomaly/birth defect;
- Is a new cancer (that is not a condition of the study);
- Is associated with an overdose;
- Is another important medical event

Exceptions to Serious Adverse Event Reporting include events related to progression of the cancer under study, including hospitalization or death. These events are not to be reported as serious adverse events. Hospitalization related to convenience (e.g. transportation issues, etc.) will not be considered an SAE. Any serious adverse event, or follow up to a serious adverse event, including death due to any cause other than progression of the cancer under study that occurs to any subject from the time the consent is signed through 90 days following cessation of treatment, or the initiation of new anti-cancer therapy, whichever is earlier, whether or not related to Merck product, must be reported within 2 business days of investigator knowledge to Merck Global Safety.

Additionally, any serious adverse event, considered by an investigator who is a qualified physician to be related to Merck product that is brought to the attention of the investigator at any time outside of the time period specified in the previous paragraph also must be reported immediately to Merck.

SAE reports and any other relevant safety information are to be forwarded to the Merck Global Safety [contact]

A copy of all 15 Day Reports and Annual Progress Reports is submitted as required by FDA, European Union (EU), Pharmaceutical and Medical Devices agency (PMDA) or other local regulators. Investigators will cross reference this submission according to local regulations to the Merck Investigational Compound Number (IND, CSA, etc.) at the time of submission. Additionally investigators will submit a copy of these reports to Merck & Co., Inc. (Attn: Worldwide Product Safety; [contact]) at the time of submission to FDA.

All subjects with serious adverse events must be followed up for outcome.

6.7 Reporting of Events of Clinical Interest (ECI)

Selected non-serious and serious adverse events are also known as Events of Clinical Interest (ECI) as defined below and must be reported within 2 business days to Merck Global Safety. (Attn: Worldwide Product Safety; [contact]).

For the time period beginning when the consent form is signed until treatment allocation/randomization, any ECI, or follow up to an ECI, that occurs to any subject must be reported within 2 business days to Merck Global Safety if it causes the subject to be excluded from the trial, or is the result of a protocol-specified intervention, including but not limited to washout or discontinuation of usual therapy, diet, placebo treatment or a procedure.

For the time period beginning at treatment allocation/randomization through 90 days following cessation of treatment, or 30 days following cessation of treatment if the subject initiates new

anticancer therapy, whichever is earlier, any ECI, or follow up to an ECI, whether or not related to Merck product, must be reported within 2 business days to Merck Global Safety.

Events of clinical interest for this trial include:

1. an overdose of Merck product, as defined in Section 6.3 - Definition of an Overdose for This Protocol and Reporting of Overdose to Merck, that is not associated with clinical symptoms or abnormal laboratory results.

2. an elevated AST or ALT lab value that is greater than or equal to 3X the upper limit of normal and an elevated total bilirubin lab value that is greater than or equal to 2X the upper limit of normal and, at the same time, an alkaline phosphatase lab value that is less than 2X the upper limit of normal, as determined by way of protocol-specified laboratory testing or unscheduled laboratory testing.

6.8 Evaluating Adverse Events

A qualified investigator will evaluate all adverse events according to the NCI Common Terminology for Adverse Events (CTCAE), version 4.0. Any adverse event which changes CTCAE grade over the course of a given episode will have each change of grade recorded on the adverse event worksheets. All adverse events regardless of CTCAE grade must also be evaluated for seriousness. Adverse events will be recorded, and SAE's reported, from the time of signed consent and for up to 90 days after the last treatment of MK-3475 is administered.

Table 6 Evaluating Adverse Events

An investigator, who is a qualified physician, will evaluate all adverse events as to:

V4.0 CTCAE Grading	Grade 1	Mild; asymptomatic or mid symptoms; clinical or diagnostic observations only; intervention not indicated.	
	Grade 2	Moderate; minimal, local or noninvasive intervention indicated; limiting age-appropriate instrumental ADL.	
	Grade 3	Severe or medically significant but not immediately life-threatening; hospitalization or prolongation or hospitalization indicated; disabling; limiting self-care ADL.	
	Grade 4	Life threatening consequences; urgent intervention indicated.	
	Grade 5	Death related to AE	
Seriousness	A serious adv	erse event is any adverse event occurring at any dose or during any use of Merck product that:	
	†Results in death; or		
	† Is life threatening; or places the subject, in the view of the investigator, at immediate risk of death from the event as it occurred (Note: This does not include an adverse event that, had it occurred in a more severe form, might have caused death.); or		
	†Results in a persistent or significant disability/incapacity (substantial disruption of one's ability to conduct normal life functions); or		
	†Results in or prolongs an existing inpatient hospitalization (hospitalization is defined as an inpatient admission, regardless of length of stay, even if the hospitalization is a precautionary measure for continued observation. (Note: Hospitalization for an elective procedure to treat a pre-existing condition that has not worsened is not a serious adverse event. A pre-existing condition is a clinical condition that is diagnosed prior to the use of a Merck product and is documented in the patient's medical history.); or		
	† Is a congenital anomaly/birth defect (in offspring of subject taking the product regardless of time to diagnosis);or		
	Is a new cancer (that is not a condition of the study) (although not serious per ICH definition, is reportable to Merck within 2 working days to meet certain local requirements); or		
		se (whether accidental or intentional). Any adverse event associated with an overdose is considered a serious adverse event for collection purposes. An is not associated with an adverse event is considered a non-serious event of clinical interest and must be reported to Merck within 2 working days.	

	Other important medical events that may not result in death, not be life threatening, or not require hospitalization may be considered a serious adverse event when based upon appropriate medical judgment, the event may jeopardize the subject and may require medical or surgical intervention to prevent one of the outcomes listed previously (designated above by a †).		
Duration	Record the start and stop dates of the adverse event. If less than 1 day, indicate the appropriate length of time and units		
Action taken	Did the adverse event cause Merck product to be discontinued?		
Relationship to Merck Product	Did Merck product cause the adverse event? The determination of the likelihood that Merck product caused the adverse event will be provided by an investigator we is a qualified physician. The investigator's signed/dated initials on the source document or worksheet that supports the causality noted on the AE form, ensures that medically qualified assessment of causality was done. This initialed document must be retained for the required regulatory time frame. The criteria below are intend as reference guidelines to assist the investigator in assessing the likelihood of a relationship between the test drug and the adverse event based upon the availal information. The following components are to be used to assess the relationship between Merck product and the AE; the greater the correlation with the components and the respective elements (in number and/or intensity), the more likely Merck product caused the adverse event (AE):		
	respective eleme	ents (in number and/or intensity), the more likely Merck product caused the adverse event (AE): Is there evidence that the subject was actually exposed to Merck product such as: reliable history, acceptable compliance assessment (pill count,	

Relationship	The following components are to be used to assess the relationship between the test drug and the AE: (continued)	
to Merck Product	Dechallenge	Was Merck product discontinued or dose/exposure/frequency reduced?
(continued)		If yes, did the AE resolve or improve?
(continueu)		If yes, this is a positive dechallenge. If no, this is a negative dechallenge.
		(Note: This criterion is not applicable if: (1) the AE resulted in death or permanent disability; (2) the AE resolved/improved despite continuation of the investigational product; or (3) the trial is a single-dose drug trial); or (4) investigational product(s) is/are only used one time.)
	Rechallenge	Was the subject re-exposed to Merck product in this study?
		If yes, did the AE recur or worsen?
		If yes, this is a positive rechallenge. If no, this is a negative rechallenge.
		(Note: This criterion is not applicable if: (1) the initial AE resulted in death or permanent disability, or (2) the trial is a single-dose drug trial); or (3) investigational product(s) is/are used only one time).
		NOTE: IF A RECHALLENGE IS PLANNED FOR AN ADVERSE EVENT WHICH WAS SERIOUS AND WHICH MAY HAVE BEEN CAUSED BY MERCK PRODUCT, OR IF REEXPOSURE TO MERCK PRODUCT POSES ADDITIONAL POTENTIAL SIGNIFICANT RISK TO THE SUBJECT, THEN THE RECHALLENGE MUST BE APPROVED IN ADVANCE BY THE SPONSOR-INVESTIGATORAS PER DOSE MODIFICATION GUIDELINES IN THE PROTOCOL.
	Consistency with Trial Treatment Profile	Is the clinical/pathological presentation of the AE consistent with previous knowledge regarding Merck product or drug class pharmacology or toxicology?
The assessment o above elements.	f relationship will l	be reported on the worksheets by an investigator who is a qualified physician according to his/her best clinical judgment, including consideration of the
Record one of th	e following	Use the following scale of criteria as guidance (not all criteria must be present to be indicative of Merck product relationship).
Yes, there is a re possibility of Me relationship.		There is evidence of exposure to Merck product. The temporal sequence of the AE onset relative to the administration of Merck product is reasonable. The AE is more likely explained by Merck product than by another cause.

No, there is not a reasonable	Subject did not receive the Merck product OR temporal sequence of the AE onset relative to administration of Merck product is not reasonable OR	
possibility of Merck product relationship	the AE is more likely explained by another cause than the Merck product. (Also entered for a subject with overdose without an associated AE.)	
relationship		

6.8.1 Sponsor-Investigator Responsibility for Reporting Adverse Events

The sponsor-investigator is required to report all problems, events and information that require prompt reporting to the IRB within ten (10) calendar days of learning of the problem.

Adverse events will be reported from the time of signing of consent up until 90 days following the last dose of MK-3475.

Laboratory abnormalities will be recorded as adverse events only if they meet the following criteria: the abnormality is symptomatic, warrants a change to study drug dosing, is designated clinically significant by the investigator, or reaches severity of grade 3 or higher (asymptomatic lab values < grade 3 will not be recorded as AEs).

If a problem, event or information is determined to be an unanticipated problem involving risks to participants or others, it will be reviewed by the convened IRB, appropriate steps will be taken and it will be reported to appropriate institutional and governmental officials as provided under applicable law.

For the purposes of this protocol, the terms Adverse Event, Serious Adverse Event (Related, Possibly Related or Unexpected) and Unanticipated Problem are defined in accordance with Fred Hutchinson Cancer Research Center Institutional Review Board Policy 2.6, version 6.03.

7.0 STATISTICAL ANALYSIS PLAN

This study administers therapy to two groups of patients, relapsed/refractory FL and relapsed/refractory DLBCL.

Subjects who fail to complete study therapy or withdraw consent before the first response assessment for reasons other than disease progression, death, SAE, or drug-related adverse events will be replaced, to allow response assessment in accordance with study stopping rules. The first group (Arm A) includes patients with relapsed or refractory follicular lymphoma, and will include at least 9 patients with rituximab-refractory disease.

The second group (Arm B) consists of patients with relapsed/refractory diffuse large B-cell lymphoma ineligible for, or failing to respond to or progressing, after autologous stem cell transplantation.

These groups will employ independent rules, using Simon's two-stage design, and accrual will be suspended for review if futility thresholds are met. Two-stage designs which limit the maximum sample size will be considered. Once enrollment is suspended, the nature of events to leading to stopping will be assessed by the Principal Investigator and reported to institutional regulatory authorities, in accordance with the institutional Data Safety Monitoring Plan. The institutional Data Safety Monitoring Committee will determine whether any further accrual may proceed. Statistical analysis will entail descriptive statistics. Categorical variables will be summarized by number and percentage, and continuous variables will be summarized by min/median/max/mean/sd, respectively. Overall response rate, and response quality, will be evaluated according to CT criteria and PET/CT in relevant patients, as per the 2014 Lugano criteria.²⁸ PFS/OS distribution will be estimated and Kaplan-Meier curves will be presented. Log-rank testing and Cox proportional hazard regression models might be applied to evaluate the association between survival endpoints and prognostic factors. To compare continuous variable in the correlative studies, student's t-test and regression analysis might be applied if deemed appropriate.

Subjects who fail to complete study therapy before the first response assessment for reasons other than disease progression, death, SAE, or drug-related adverse events will be replaced, to allow response assessment in accordance with study stopping rules.

7.1. Study Stopping Rules: Efficacy

7.1.1. Arm A: Relapsed/refractory FL

The following assumptions will underlie the two-stage design for Arm A: At the end of induction response rate will be 60% with this combination, against a null hypothesis of 30%. With this 2-stage design, 7 patients will be enrolled in the first stage. If 2 or fewer respond among these 7 patients, enrollment to this study arm will be stopped. Otherwise, 13 additional patients will be accrued in the second stage for a total of 20. The null hypothesis will be rejected if 10 or more responses are observed in 20 patients. This design yields a type I error rate of .05 and a power of 0.82 when the true response is 60%.

A goal of 9 rituximab-refractory FL patients will be included in this arm. The proposed response rate is hypothesized to be no different among these patients (60%). Enrollment will be adjusted to permit enrollment of these patients without over-accruing to the study. The 95% confidence interval for the proposed 60% response rate in 9 rituximab-refractory FL patients is 28-92%. Thus, by enrolling 9 rituximab-refractory patients, this study will reasonably exclude a response rate of <30% in this subgroup.

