2.3 Exploratory Objectives

- (1) To explore correlates of response using peripheral blood flow cytometry.
- (2) To evaluate the PDL1/PD1 axis and tumor microenvironment, using biopsies performed at baseline, between cycles 1 and 3, and at the time of persistent/progressive disease (optional).
- (3) Explore treatment outcomes in subsets of enrolled patients with rituximab-refractory follicular lymphoma

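### Nine rituximab-refractory patients in Arm A do not reasonably exclude a response rate below 30%: the plan's own 95% interval starts at 28%, and the chance of exclusion at a true 60% is 0.23 to 0.48

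*Combined protocol and SAP*

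**What the plan says.** Section 7.1.1 designs Arm A as a two-stage trial: "At the end of induction response rate will be 60% with this combination, against a null hypothesis of 30" per cent. It then turns to a subgroup: "A goal of 9 rituximab-refractory FL patients will be included in this arm". The same 60% response rate is assumed there. The precision statement is: "The 95% confidence interval for the proposed 60% response rate in 9 rituximab-refractory FL patients is 28-92" per cent. From this the section infers that, with 9 such patients, "this study will reasonably exclude a response rate of <30% in this subgroup".

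The opening of section 7.0 words the number differently, saying that Arm A "will include at least 9 patients with rituximab-refractory disease". Section 2.3 lists the subgroup among the exploratory objectives: "Explore treatment outcomes in subsets of enrolled patients with rituximab-refractory follicular lymphoma". No interval method is named for the subgroup, no probability of exclusion is given, and no decision rule is attached to it.

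**The concern.** The last sentence is presented as a consequence of the interval before it, yet an interval that starts at 28% does not rule out every rate below 30%. The two-point gap also understates the problem, because the interval is evaluated at a response count that 9 patients cannot produce.

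The sentence is the only statistical argument offered for a subgroup of 9, and section 7.1.1 says enrollment will be adjusted to obtain these patients. The 30% benchmark is also Arm A's null rate. A reader could therefore take the sentence as a planned efficacy inference in rituximab-refractory disease and carry it into a report. With no method named, whether 6 of 9 responses supports the claim could be settled after the data are seen.

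**Working it through.** **Inputs.** Subgroup size n = 9, assumed true rate 0.60, rate to exclude 0.30, confidence level 95%, all from section 7.1.1. The intervals are taken as two-sided, and all 9 patients as evaluable.

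**Step 1: reproduce the stated interval.** Wald formula, p ± 1.96 × √(p(1 − p)/n):

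0.60 ± 1.96 × √(0.24/9) = 0.60 ± 0.320 = 0.280 to 0.920.

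This matches 28-92%. It corresponds to 0.60 × 9 = 5.4 responders. With the same formula at exactly 60%, the lower limit is 0.296 at n = 10 and first passes 0.30 at n = 11 (0.310).

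**Step 2: lower 95% limits at attainable counts, n = 9.** The Clopper-Pearson lower limit is the 2.5% point of a Beta(x, n − x + 1) distribution.

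| Responses | Observed rate | Clopper-Pearson | Wald | Wilson |
|---|---|---|---|---|
| 5/9 | 55.6% | 21.2% | 23.1% | 26.7% |
| 6/9 | 66.7% | 29.9% | 35.9% | 35.4% |
| 7/9 | 77.8% | 40.0% | 50.6% | 45.3% |

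At 5/9 none of the three excludes 30%. At 6/9 the answer depends on the method. At 7/9 all three exclude it. The Clopper-Pearson result at 6/9 is a near miss: the limit is 0.2993, and P(X ≥ 6 | n = 9, p = 0.30) = 0.0253 against the 0.025 needed.

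**Step 3: chance of exclusion at a true rate of 60%.** With X ~ Binomial(9, 0.60):

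- P(X = 6) = 0.2508, P(X = 7) = 0.1612, P(X = 8) = 0.0605, P(X = 9) = 0.0101.
- Clopper-Pearson needs at least 7: 0.1612 + 0.0605 + 0.0101 = 0.232 (from unrounded terms).
- Wald or Wilson needs at least 6: 0.2508 + 0.2318 = 0.483.
- P(X ≤ 5) = 0.517, so exclusion fails more often than not under each of the three.

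Agresti-Coull, Jeffreys and one-sided 95% limits (exact or Wald) also need at least 6/9 and give the same 0.483.

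**Step 4: more than 9 patients.** Section 7.0 treats 9 as a minimum. Chance of excluding 30% at a true 60%, with the responses needed in parentheses:

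| n | Clopper-Pearson | Wald | Wilson |
|---|---|---|---|
| 9 | 0.23 (7) | 0.48 (6) | 0.48 (6) |
| 10 | 0.38 (7) | 0.38 (7) | 0.63 (6) |
| 11 | 0.53 (7) | 0.53 (7) | 0.53 (7) |
| 12 | 0.44 (8) | 0.67 (7) | 0.67 (7) |
| 13 | 0.57 (8) | 0.57 (8) | 0.57 (8) |
| 20 | 0.76 (11) | 0.76 (11) | 0.76 (11) |

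The last row is an upper bound in which every Arm A patient is rituximab-refractory. The plan does not describe that case.

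**The case against.** The interval itself is computed correctly, the shortfall is two points, and the claim is hedged with the word reasonably. The subgroup is exploratory, section 7.0 describes the analysis as descriptive, and nothing in Arm A's test turns on it. The plan claims no power for the subgroup; the probability of exclusion is a yardstick brought to it from outside. The figure of 0.23 belongs to a method the plan did not use and depends on a margin of 0.0007 at 6/9; on the plan's own Wald basis the figure is 0.48. At a true 60%, 5/9 and 6/9 are equally likely (0.2508 each), so an illustration that looks only at 5/9 would be one-sided. A few more patients can raise the chance to 0.63 (Wilson, n = 10) or 0.67 (Wald or Wilson, n = 12).

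Most of this stands as a limit on importance. It does not rescue the sentence. The sentence says what enrolling 9 patients will achieve and ties it to a 95% interval; a property that holds in 23% to 48% of cases is not reasonably assured. The method-independent point remains that an interval from 28% does not exclude 28-30%. A looser criterion would support the wording: a one-sided 90% exact limit is 0.301 at 5/9, with probability 0.733. The plan, however, cites a 95% interval.

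**Conclusion.** The concern holds. The stated conclusion contradicts the interval it rests on, and 9 patients do not have the property claimed for them. At a true rate of 60% the chance of excluding 30% is 0.23 with Clopper-Pearson and 0.48 with Wald or Wilson.

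These figures assume exactly 9 evaluable patients and two-sided 95% intervals. They ignore a stage 1 stop of Arm A (2 or fewer responses in 7, probability 0.096 at a true 60%), which would leave fewer than 9. The 0.23 is sensitive to the method because of the near miss at 6/9; the conclusion that exclusion fails more often than not is the same for all three methods.

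The text should be corrected, but the consequence is small: Arm A's primary rule of 10 or more responses in 20 is unaffected.

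**What to change.** Replace the last two sentences of section 7.1.1 with text such as:

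> With 9 rituximab-refractory patients, exact (Clopper-Pearson) 95% confidence intervals would be 21.2-86.3% for 5 responses, 29.9-92.5% for 6 and 40.0-97.2% for 7. On these intervals a rate below 30% would be excluded only with 7 or more responses (probability 0.23 if the true rate is 60%). This subgroup analysis is exploratory and descriptive, and the interval will be computed on the number of rituximab-refractory patients actually evaluable.

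Clopper-Pearson is a choice. If the study team prefers Wilson, it should name that method in advance and change the intervals, the threshold (6 or more) and the probability (0.48) to match. Deleting the concluding sentence alone would remove the contradiction, but would leave the interval method unstated.

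Separately, make sections 7.0 and 7.1.1 agree on whether 9 is a minimum or a goal.

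The cost is SAP wording and a less favourable statement about the subgroup. Arm A's sample size and primary test do not change.
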